4.3. Sample Size

4.3.1. Patient sample requirement

The primary objective of this study is to estimate the retention rate of RA patients' treatment with abatacept over 24 months in routine clinical practices in each participating country with a sufficient level of precision.

Based on the extent of biologics' use in each participating country (BMS market research data) and feasibility considerations, it is estimated that each country will be able to enrol the following number of patients over the planned 2-year accrual period (for each treatment line of abatacept and for each enrolment period). The figures vary between 26% and 45% of the estimated total number of patients to be treated with abatacept in the respective countries (see [Table 1](#)) in second or further line:

Table 1 Patients number expected by country and by study period

Countries	Number of patients in second or further treatment line of abatacept*after failure of one or more TNF (Accrual period 2008- 2010)		Number of patients expected in first treatment line of abatacept**after failure to DMARD including MTX (Accrual period up to June. 2013)	Number of patients expected in second or further treatment line of abatacept* (Accrual period up to Dec 2013)
	Expected	Real (cut off Dec 2010)		
Germany	370	398	150	150
Italy	200	235	100	100
Greece	120	152	60	60
The Netherlands	100	34	25	25
Belgium	60	15	50	NA
Austria	50	51	20	25
Ireland	30	0	NA	NA
Denmark	25	7	NA	NA
Canada	200***	233	NA	NA
France	NA	NA	220	400
Spain	NA	NA	120	120
Czech Republic	20	26	NA	NA
Switzerland	NA	NA	10	40
TOTAL	1175	1151	755	920

* In Europe, abatacept in combination with methotrexate is indicated for the treatment of moderate to severe active rheumatoid arthritis in adult patients who have had an insufficient response or intolerance to other disease-modifying anti-rheumatic drugs including at least one tumour necrosis factor inhibitor.

** In Europe, abatacept, in combination with methotrexate is indicated for the treatment of moderate to severe active rheumatoid arthritis in adult patients who responded inadequately to previous therapy with one or more Disease-Modifying Anti-Rheumatic Drugs including methotrexate or TNF-alpha inhibitor.

*** In Canada, abatacept is indicated for reducing signs and symptoms, including clinical responses, inhibiting the progression of structural damage, and improving physical function in adult patients with moderately to severely active rheumatoid arthritis who have had an inadequate response to one or more Disease-Modifying Anti-Rheumatic Drugs and/or to Tumor Necrosis Factor antagonists. Abatacept may be used as monotherapy or in combination with DMARD therapy.

Above initial assumptions were estimated based on existing data. These assumptions would be updated according to the real extent of biologics' use in each participating country and to evolution of feasibility of the study during the enrolment period. In some countries this estimated number of enrolled patient could be either increased or decreased.

The overall number of patients in this study from the countries listed above will be around 2825 patients.

The estimated 2-year retention rate was between 60% and 70% based on the ATTAIN study²⁶ in patients who had an inadequate response to at least one tumour necrosis factor inhibitor corresponding to an abatacept discontinuation rate between 30% and 40 %. Since the retention rate in clinical practice is usually lower than that in randomized controlled trials¹¹, we hypothesize the retention rate in this study will be about 60%. With a sample size of 370 patients in Germany, one can expect the observed retention rate to be within $60\% \pm 5\%$.

Assuming that the sample size of each country will vary from 20 to 400 patients who had an inadequate response to at least one tumour necrosis factor inhibitor, the level of precision for the country-specific estimates will be proportionally decreased. The data from different countries may be pooled if appropriate.

The estimated 2-year retention rate was around 80% based on the AIM study³⁷ in abatacept-treated patients who had an inadequate response to Methotrexate corresponding to an abatacept discontinuation rate of around 20%. Since the retention rate in clinical practice is usually lower than that in randomized controlled trials¹¹, we hypothesize the retention rate in this study will be about 65% to 75%. Assuming that the sample size of each country will vary from 10 to 220 patients who had an inadequate response to at least one DMARD including Methotrexate or TNF α inhibitor, the level of precision for the country-specific estimates will be low. Therefore the data from countries may be pooled to increase the precision up to 3.0 to 3.5%.

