3.2. Study Population

3.2.1. Sampling Plan

The study will be proposed to rheumatologists at either hospital or private practice. Treatment should be initiated and supervised by specialist physicians experienced in the diagnosis and treatment of rheumatoid arthritis.

A two-stage recruitment strategy will be implemented, with patient recruitment following a center selection procedure.

Selection and recruitment of a national sample of centers:

A general list of rheumatologists (centers) will be compiled (BMS data on file) in each country:

- Approximately 700-1400 in Germany
- Approximately 200 in Austria
- Approximately 242 in Belgium
- Approximately 52 in Czech Republic
- Approximately 300 in Greece
- Approximately 880 in Italy
- Approximately 230 in the Netherlands
- Approximately 55 in Ireland
- Approximately 120 in Denmark
- Approximately 231 in Canada
- Approximately 700 in France
- Approximately 800 in Spain
- Approximately 70 in Switzerland

A letter will be sent to centers with an overall description of the study and an enquiry on potential interest to participate. Rheumatologists will be invited to participate in the study by a letter signed and mailed by Bristol-Myers Squibb. It is assumed that a minimum response rate of 10-20% will be obtained (as not all centers on the general list of centers are treating patients with biologics). To estimate the actual response rate, a small number of invitation letters will be sent to a subset of rheumatologists first. The number of additional letters to be sent out in order to recruit the required number of rheumatologists will be determined accordingly. Rheumatologists will be stratified by country. Obtained responses, either positive or negative, will be tracked and recorded. If the targeted number of rheumatologists is not reached after mailing, non-responding rheumatologists will be contacted by phone, within each stratum, until the targeted number is reached.

Rheumatologists will be requested to provide a brief description to characterize their center: by treatment setting (private rheumatologists or hospital, or institutions), geography (large city or town, $\geq 100,000$ inhabitants, vs. small town), type of institution (academic vs. non academic), number of physicians providing care to RA patients, and volume of patients. Site eligibility will be determined based on site willingness to participate.

Selection of patient cohort:

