4.3.2. Rheumatologist sample requirement

Internal data (BMS data on file) show that hospital based rheumatologists declare an average of 20 RA patients cared for per month and private practice rheumatologists declare an average of 12 RA patients cared for per month. It also appears that a majority of these RA patients are treated with a DMARD. The average number of patients that participating rheumatologists will be able to include during the accrual period was estimated at 6 patients for patients who had an inadequate response to at least one tumour necrosis factor inhibitor. To take into account differences in recruitment capacity of the rheumatologists, the duration of the accrual period was set to 2 years and the maximum patient accrual will be set to 10 for each treatment line of abatacept.

To estimate the number of sites to be invited to participate in the study, we assume a minimum of 10% participation rate and among the participating sites, a minimum of 20% of inactive sites. However, as detailed in [section 3.2.1 Sampling Plan](#), the actual number of invited sites per country will depend on the response rate obtained after contacting an initial small set of centers. A total of 2825 patients will be enrolled over a maximum 18-24 months period (for each

treatment line of abatacept and for each enrolment period) to follow-up over 2 years; and at the latest in December 2013.

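### The planned precision in section 4.3.1 assumes independent patients, although patients are recruited in clusters within rheumatologists

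*Protocol*

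**What the plan says.** Section 4.3.1 gives two precision statements for 24-month retention.

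- Second or further line: the protocol says "we hypothesize the retention rate in this study will be about 60" per cent, and then "With a sample size of 370 patients in Germany, one can expect the observed retention rate to be within" 60% ± 5%.
- First line: it says "we hypothesize the retention rate in this study will be about 65% to 75" per cent, concedes that single-country precision will be low, and continues: "Therefore the data from countries may be pooled to increase the precision up to 3.0 to 3.5" per cent. The pooled first-line sample is the third figure in the last row of Table 1: "TOTAL 1175 1151 755 920".

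Neither statement mentions a design effect, an intra-cluster correlation or clustering.

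Section 3.2.1 describes the sampling: "A two-stage recruitment strategy will be implemented, with patient recruitment following a center selection procedure". Sections 3.2.1 and 3.6.2 have each rheumatologist enrol consecutive eligible patients, with a limit of 10 for each treatment line. Section 4.3.2 adds: "The average number of patients that participating rheumatologists will be able to include during the accrual period was estimated at 6 patients". That mean is given only for patients with an inadequate response to a TNF inhibitor; no mean is given for first line.

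**The concern.** Patients of one rheumatologist share that physician's habits on when to stop a biologic, as well as local access and case mix. Retention may therefore be correlated within centre. If it is, a sample of 370 patients from roughly 60 centres (370 / 6 ≈ 62) carries less information than 370 independent patients, and a margin from the simple binomial formula is too small.

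This matters because the primary objective is estimation. There is no primary hypothesis test, and section 4.3.1 opens by asking for a sufficient level of precision in each country. The margins are the main quantitative support for the sample size. Section 4.3.2 then sets the expected number of patients per rheumatologist, but the two sections are never connected.

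**Working it through.** **Inputs from the protocol.** Retention p = 0.60 (second or further line) and 0.65 to 0.75 (first line), section 4.3.1. Germany n = 370, section 4.3.1. Pooled first line n = 755, Table 1 (150 + 100 + 60 + 25 + 50 + 20 + 220 + 120 + 10 = 755). Mean of 6 patients per rheumatologist and cap of 10, section 4.3.2. Section 4.3.1 names no confidence level; section 4.2 uses 95%, and that level reproduces the stated figures.

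**Inputs that are assumptions.** ICC from 0.01 to 0.10, since the protocol gives none. Six patients per centre in first line, borrowed from the other treatment line.

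**Step 1: reproduce the stated margins.** Half-width = 1.96 × √(p(1−p)/n).

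- Germany: 1.96 × √(0.6 × 0.4 / 370) = 4.99 points. The n needed for exactly ±5 is 369.
- Pooled first line: 1.96 × √(0.65 × 0.35 / 755) = 3.40 points; 1.96 × √(0.75 × 0.25 / 755) = 3.09 points.

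Both match the protocol with a design effect of exactly 1.

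**Step 2: allow for clustering.** Design effect = 1 + (m−1) × ICC, and each half-width is multiplied by its square root. With m = 6:

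| ICC (assumed) | Design effect | Germany, n = 370 | n needed for ±5 | First line, n = 755 (p = 0.75 to 0.65) |
|---|---|---|---|---|
| 0 | 1.00 | ±4.99 | 369 | 3.09–3.40 |
| 0.01 | 1.05 | ±5.12 | 388 | 3.16–3.49 |
| 0.02 | 1.10 | ±5.24 | 406 | 3.24–3.57 |
| 0.05 | 1.25 | ±5.58 | 461 | 3.45–3.80 |
| 0.10 | 1.50 | ±6.11 | 554 | 3.78–4.17 |

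If every centre were at the cap (m = 10), the German margin would be ±5.21 / 5.42 / 6.01 / 6.88 at the four positive ICC values. That is an upper bound, not an expectation. Unequal centre sizes around a mean of 6 would raise the design effect somewhat above the values in the table.

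**Step 3: where the stated figures give way.** At m = 6 and n = 370 the German margin reaches 5.5, and so rounds to 6, at ICC = ((5.5/4.99)² − 1)/5 ≈ 0.043. The pooled first-line margin at p = 0.65 passes 3.5 at ICC = ((3.5/3.40)² − 1)/5 ≈ 0.012.

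**Step 4: Germany with the enrolment in Table 1.** Table 1 reports 398 German patients actually enrolled in second or further line by December 2010, and plans 150 more by December 2013 (398 + 150 = 548). With p = 0.60 and m = 6:

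| ICC (assumed) | n = 398 | n = 548 |
|---|---|---|
| 0 | ±4.81 | ±4.10 |
| 0.01 | ±4.93 | ±4.20 |
| 0.02 | ±5.05 | ±4.30 |
| 0.05 | ±5.38 | ±4.59 |
| 0.10 | ±5.89 | ±5.02 |

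**The case against.** The case on the other side has real weight.

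- **German enrolment exceeds 370.** A reader who sees 369 needed against 370 planned might infer that there is no slack. Table 1 contradicts that. Section 2.1 defines the objective by country and treatment line, not by enrolment period, so 548 patients may contribute. On that footing ±5 is essentially kept at m = 6 over the whole assumed ICC range. This stands, with one caveat: centres that recruit in both periods could average more than 6 patients.
- **The size is assumed.** At ICC 0.01 to 0.02 with 6 per centre, the loss at n = 370 is only about 0.1 to 0.25 points, and the result still rounds to ±5. This stands.
- **The first-line figures need a borrowed cluster size.** This also stands. The protocol's wording there is also that of a best case ("may be pooled to increase the precision up to 3.0 to 3.5" per cent). Yet the stated range is what independent patients would give, and at p = 0.65 a small positive ICC exceeds it.
- **The analysis may handle clustering.** A reader might infer that the reported 95% intervals will be too narrow. The protocol does not support that: section 4.2 names no variance method and leaves detail to a separate statistical plan. That plan cannot, however, correct a margin stated in the protocol.
- **No decision depends on ±5.** Country numbers come from market data and feasibility, so the correction changes no recruitment target. This limits the consequence but does not make the stated precision right.

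**Conclusion.** The point holds as a statement about planned precision in section 4.3.1. Both margins rest on an unstated independence assumption that the protocol's own two-stage sampling does not support. They are too narrow if retention correlates within centre, and by how much depends on an ICC that the protocol does not give.

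Over the assumed range of 0.01 to 0.10 with 6 patients per centre, Germany at n = 370 moves from ±5.0 to between ±5.1 and ±6.1 points. Pooled first line moves from 3.1–3.4 to between 3.2–3.5 and 3.8–4.2 points. The German shortfall shrinks at n = 398 and largely or wholly disappears if both enrolment periods are combined. The first-line margin has no such offset in Table 1.

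Two further readings should be avoided. This is not an arithmetic error: the binomial calculation is correct for independent patients. Nor does the protocol describe clusters of 6 to 10: 6 is an expected mean for one treatment line and 10 is a cap.

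**What to change.** In section 4.3.1, restate each margin with a design effect of 1 + (m−1) × ICC over a stated ICC range. Use the current sample sizes (for Germany 398, or 548 if the enrolment periods are combined). State the assumed number of patients per centre for first line separately, because section 4.3.2 does not give one.

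In section 4.2, specify that the confidence intervals for retention will use a centre-clustered variance. Sections 4.4.1 and 4.4.2 already collect the centre number, so no new data are needed.

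The cost is a few sentences and a routine software option. The downside is that the stated precision becomes slightly less favourable. No recruitment target has to change.

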4.3.2. Rheumatologist sample requirement

Internal data (BMS data on file) show that hospital based rheumatologists declare an average of 20 RA patients cared for per month and private practice rheumatologists declare an average of 12 RA patients cared for per month. It also appears that a majority of these RA patients are treated with a DMARD. The average number of patients that participating rheumatologists will be able to include during the accrual period was estimated at 6 patients for patients who had an inadequate response to at least one tumour necrosis factor inhibitor. To take into account differences in recruitment capacity of the rheumatologists, the duration of the accrual period was set to 2 years and the maximum patient accrual will be set to 10 for each treatment line of abatacept.

To estimate the number of sites to be invited to participate in the study, we assume a minimum of 10% participation rate and among the participating sites, a minimum of 20% of inactive sites. However, as detailed in [section 3.2.1 Sampling Plan](#), the actual number of invited sites per country will depend on the response rate obtained after contacting an initial small set of centers. A total of 2825 patients will be enrolled over a maximum 18-24 months period (for each

treatment line of abatacept and for each enrolment period) to follow-up over 2 years; and at the latest in December 2013.

4.4. Collected data

4.4.1. Participating rheumatologists

- Rheumatologist identification (center number, name, surname, sex, address, e-mail address)
- Description of the center:
 - Treatment setting (community vs. hospital)
 - Geography (region, large city or town (> 100,000 inhabitants) vs. small towns)
 - Type of institution (academic vs. non-academic)
 - Number of rheumatologists providing care to RA patients
 - Volume of patients

4.4.2. Patients

- Patient identification (N° center, N° patient)
- Data collected retrospectively at baseline (first administration of abatacept IV)
 - Socio-demographics
 - Disease history and characteristics
 - Prior RA treatments (biologic and conventional DMARDs, other concomitant medication)
- Data collected prospectively from baseline:
 - Clinical outcomes: DAS28 and its individual components (SJC, TJC, CRP/ESR), HAQ-DI, Physician's global assessment,
 - Patient-reported outcomes: Patient Global Assessment, Patient satisfaction, Pain (see Appendix)
 - Abatacept dosage and frequency of administration (IV and SC formulation)
 - Reasons and subsequent RA treatment with conventional/biologic DMARDs if abatacept treatment was discontinued for 6 months after discontinuation
 - Reason for change in the route of administration of abatacept (from IV to SC)
 - Other concomitant medication for RA
 - Adverse Drug Reactions

4.5. Data Set Description

4.5.1. Patient data sets

The data set will consist of all patients recruited, excluding those with missing data related to the patient's sex and age.

4.5.2. Rheumatologist data sets

Due to the sampling technique, the sampling database will be split into 3 different rheumatologist data sets:

Responding rheumatologists agreeing to participate in the study

Responding rheumatologists refusing to participate in the study

Non-responding rheumatologists

Rheumatologists agreeing to participate will be further split into 2 different populations:

Active rheumatologists, who included at least one evaluable patient

Non-active rheumatologists.

5. STUDY CONDUCT

5.1. Ethics

This study will be conducted in accordance with the ethical principles that have their origin in the Declaration of Helsinki and will be consistent with International Conference on Harmonization Good Clinical Practice (ICH GCP), Good Epidemiological Practices (GEP) and applicable regulatory requirements taking into account that this is an observational, non-interventional trial.

The study will be conducted in compliance with the protocol.

The rights, safety and well-being of the study patients are the most important considerations and should prevail over interests of science and society.

Study personnel involved in conducting this trial will be qualified by education, training, and experience to perform their respective task(s).

This study will not use the services of study personnel where sanctions have been invoked or where there has been scientific misconduct or fraud (e.g., loss of medical licensure, debarment).

Systems with procedures that assure the quality of every aspect of the study will be implemented.

The study will be conducted according to the local regulations and ethical considerations applicable.

The data collection method will comply with the privacy and confidentiality requirements applicable in local participating countries. There will be agreement between BMS and the investigators regarding the confidentiality of the data. Qualified representatives on behalf of BMS may monitor the patient medical records in order to determine the accuracy of the data, and these persons will treat the information as confidential. The patient identity (name, address and other identifiers) will not be collected and will remain confidential. In the database of the CRO in charge, patients will only be referred to by a code number. Only the investigators will be able to link the code number to the name of the patients.

5.2. Responsibilities within the Study

5.2.1. Compliance with the Protocol and Protocol Revisions

The study shall be conducted as described in this approved protocol. All revisions to the protocol must be discussed with, and be prepared by BMS. The protocol authors should not implement any deviation or change to the protocol without prior review.

5.2.2. Monitoring for protocol compliance

Data reported on the CRF must be consistent with the source documents and plausible.

The confidentiality of records that could identify patients must be protected, respecting the privacy and confidentiality rules in accordance with the applicable regulatory requirement(s).

Representatives of BMS may be allowed to visit sites to assess the data quality and study integrity. On site, they will indirectly review study records, via the participating physician, compare them with source documents, discuss the conduct of the study with the physician, and verify that the facilities remain acceptable.

In addition, the study may be evaluated by BMS internal auditors and government inspectors who must be allowed indirect access to CRFs, source documents and other study files.

5.2.3. Records and reports

A correction must be made by striking through the incorrect entry with a single line and entering the correct information adjacent to the incorrect entry. The correction must be dated, initialled and explained (if necessary) by the person making the correction and must not obscure the original entry.

The completed CRF must be promptly reviewed, signed, and dated by the participating physician.

5.2.4. Study Organization

The following roles and responsibilities are detailed below (see Table 2):

Table 2 Study organization

BMS Staff	GEOR Department GMA Local medical departments	Design of the protocol and the data collection sheets, involvement in the data analysis in the presentation of the results and in their publication. Implementation and conduct of the study. Perform the analysis, report writing, responsible for publication writing, communication of the results.
-----------	---	--

